Using G*Power 3.1, sample sizes needed to detect group differences in the primary outcome (changes in accommodation from baseline to follow-up) between the BRAVE group and the Control group of small (.2), medium (.5), and large effects (.8) based on an F test, linear multiple

regression with $\alpha = .05$ and power = 0.80 were 395, 55, and 25, respectively for the primary outcome (hypothesis 1). The target sample of 300 (150 per SSI condition accounting for attrition) reflects power to detect a small to medium effect as observed by previous SSI trials.

Analytic Plan

To address *hypothesis 1*, a multiple linear regression with intervention condition (1=ORR+Project Brave; 0=ORR+waitlist control) and baseline accommodation levels (sum score of the first 9 items of the Family accommodation scale with higher scores indicating higher levels of accommodation) as predictor variables will indicate whether ORR+Project BRAVE, versus ORR+delayed SSI access, led to differential reductions in accommodation behavior from baseline to 2-week follow up. A p-value of $<.05$ will indicate a significant change in parental accommodation from baseline to 2-week follow up.

To address *hypothesis 2*, we will use the two-sample t-test to determine whether the difference between the ORR+project BRAVE and ORR+delayed SSI access group's mean ratings of the perceived post intervention condition change item is significant. A p-value of $<.05$ will indicate a significant difference between the two conditions. Descriptive statistics of the scores for both conditions will be reported as well with a mean rating above 3 (out of 5) indicating an overall, subjectively-detectable pre-to-post change.

To address *hypothesis 3*, we will examine mean scores on the Program Feedback Scale from the intervention group only. A score above 3 on any given program feedback scale item will reflect endorsement of that item (e.g. positive feedback/adequate acceptability). Thus, a mean score of 3 or higher (out of 5) across participants in this study will indicate participants found the intervention acceptable.

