For participants assigned to the ORR+ delayed SSI access group, a participant must have made it through all baseline measures (i.e., they must reach the final “page” of the baseline questionnaires, or the RCADS, though it is acceptable for the participant to leave the answer blank after seeing it) to be considered a “full completer”. For participants assigned to the ORR+Project BRAVE group, a participant must have made it through all of the intervention (i.e. they must reach the final “page” of the intervention) to be considered a full completer.

To be considered a follow-up “completer”, a participant must have made it through all of the questionnaires in the follow-up surveys (i.e. they must reach the final “page” of the follow-up questionnaires though it is acceptable for the participant to leave the answer blank after seeing it).

If the p value is greater than .05 we will assume dropout was not dependent on condition assignment and can proceed with interpreting the effects of intervention assignment. If the p value for this test is less than .05 we will conclude that dropout was dependent on condition assignment, and we will take the following steps to improve the interpretability of our results. Unequal dropout between treatment groups can introduce bias in trial results; however, this is not always the case (Bell, Kenward, Fairclough, & Horton, 2013; <https://doi.org/10.1136/bmj.e8668>). One major concern is that, if data is not missing at random, systematic differences may exist between “dropouts” and “completers” that cannot be corrected for, limiting the interpretability of our results. For example, if more control condition participants experienced a worsening of clinical symptoms and dropped out before completing follow-up measures, this worsening of symptoms would not be captured by completers’ data (or by data imputed based on the available completers’ data). Thus, should unequal dropout exist between conditions in the present study, we will report the results of our main analyses while highlighting (1) limitations to interpretation, and (2) ways in which this will inform future intervention development.

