Further, if unequal dropout is present, we will run a sensitivity analysis to determine a range of possible effect sizes for our outcomes of interest, varying how much “dropout participants” may have changed on each outcome. To establish lower- and upper-end estimates of effect size, we will: (1) calculate residual change for each of our 3 outcomes, (2) identify the 25th and 75th percentile values for residual change in each outcome, (3) run analyses for each outcome where we impute the lower residual change value (25th percentile) for all dropouts/missing data, as well as the higher residual change value (75th percentile) for all dropouts/missing data. This approach explicitly assumes data are not missing at random, providing a more unbiased estimate of the overall treatment effect in the presence of unequal dropout.

Exploratory Moderation Tests

We will also conduct exploratory moderation tests examining various baseline variables as moderators of the SSI's impact on outcome, using the same approaches to missing data and corrections for multiple tests as described elsewhere in the pre-registration

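### The dropout sensitivity runs give both arms' dropouts the same residual change, so on the natural reading they centre on a shrunken effect and are neither lower and upper ends nor less biased

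*SAP*

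**What the plan says.** Under Differential Dropout Rates, the SAP compares dropout between conditions with a Z-test: "If the p value for this test is less than .05 we will conclude that dropout was dependent on condition assignment". In that case the main results are still reported, with their limitations, and a sensitivity analysis is added.

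- Its aim: "To establish lower- and upper-end estimates of effect size".
- Its first steps: compute residual change for each outcome, then "identify the 25th and 75th percentile values for residual change in each outcome".
- Its fill-in step: "run analyses for each outcome where we impute the lower residual change value (25th percentile) for all dropouts/missing data". A second run does the same with the 75th percentile.
- Its claimed property: "providing a more unbiased estimate of the overall treatment effect in the presence of unequal dropout".

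The motivating example in the same section is "if more control condition participants experienced a worsening of clinical symptoms and dropped out before completing follow-up measures".

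The text does not say whether the residual model contains condition, whether the percentiles are taken by arm, or that the arms ever receive different values. The main models for hypotheses 1 and 4 (Analytic Plan) do contain condition and baseline. Effect sizes are Cohen's d computed from the t-values (Missing Data section).

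**The concern.** Residual change usually means follow-up regressed on baseline alone. If one percentile of that residual goes to all dropouts, the imputed data contain no arm difference among dropouts once baseline is taken into account. That is a strong assumption, it is not stated, and it is the same in both runs.

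Two descriptions in the SAP then fail. The runs are not the two ends of a range of plausible effects, because they differ only in the common value given to both arms. Nor are they in general less biased than the imputed main analysis. When the dropout test is significant, a reader would be told that the runs are the more trustworthy figures, although their centre is shrunk by construction.

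**Working it through.** The SAP gives no figure to reproduce here, so the check derives what the procedure estimates.

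**Inputs.** From the SAP: 150 per arm ("The target sample of 300 (150 per SSI condition accounting for attrition"), one common percentile per run, and a trigger at p < .05. Assumed, because the SAP does not give them: the effect, the dropout rates, residual SD of about 1 (quartiles about ±0.674), and 150 as the denominator in each arm. A negative coefficient means a larger reduction in accommodation with BRAVE.

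**Formula.** Let δ be the size of the benefit, m1 and m0 the missing fractions in BRAVE and control, and c the common residual filled in. With residuals from a pooled regression on baseline and equal arms:

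coefficient = -δ × h + (m1 - m0) × c, where h = 2(1 - m1)(1 - m0) / (2 - m1 - m0).

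The factor h is close to 1 minus the mean missing fraction. The first term is the midpoint of the two runs. The second moves them apart in opposite directions.

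**Missing at random, δ = 0.35, dropout 24% / 36%.**
- h = 2 × 0.76 × 0.64 / 1.40 = 0.695.
- Midpoint = -0.35 × 0.695 = -0.243, about 30% too small.
- Shift = 0.12 × 0.674 = 0.081.
- Runs = -0.162 (25th) and -0.324 (75th).
- Simulation (4000 trials, regression on condition and baseline): main -0.349; runs -0.16 and -0.32.

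**Other gaps.**

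| δ | Dropout BRAVE / control | h | 25th run | 75th run |
|---|---|---|---|---|
| 0.35 | 15% / 30% | 0.768 | -0.168 | -0.370 |
| 0.35 | 20% / 40% | 0.686 | -0.105 | -0.375 |
| 0.30 | 35% / 25% | 0.70 | -0.276 | -0.141 |
| 0.20 | 35% / 25% | 0.70 | -0.207 | -0.072 |

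The midpoint is shrunk in every row, by 23% to 31%. In three of the four rows, one run lies beyond the assumed effect.

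**Size of gap that triggers the analysis.** At 150 per arm the Z-test needs a gap of about 8 points from a 10% base, 10 points from 20%, and 11 points from 30% or 40%. The spread is therefore at least about 0.05 to 0.08 SD each way whenever these runs are made.

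**Cohen's d from t.** Filling in a constant residual also reduces the residual SD, so d shrinks less. At 24% / 36% and δ = 0.35 the runs are about -0.36 and -0.18, with midpoint -0.27. That is about 23% below the completers' d of -0.35, and about 7% below the d of about -0.29 obtained from the pooled t after multiple imputation with N = 300.

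**The SAP's own example, read as control leavers worsening more than BRAVE leavers.** Put control leavers 0.674 SD above their arm's expectation and leave BRAVE leavers unshifted.
- Truth = -0.35 - 0.36 × 0.674 = -0.593.
- Main analysis about -0.35; runs about -0.32 and -0.16.
- Neither run represents the scenario, because the arms never receive different values.

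**Repair.** With residuals from the condition-plus-baseline model and own-arm predictions, a common percentile gives -0.35 ± 0.12 × 0.674, that is -0.43 and -0.27, centred on the main estimate. These still miss -0.593. Opposite percentiles give -0.35 ± (0.24 + 0.36) × 0.674 = -0.35 ± 0.404, that is -0.754 and +0.054 (simulation: -0.75 and +0.05), which covers it.

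**The case against.** A reader might infer that both runs are pulled toward zero by the missing fraction. The documents do not support that. It is exact only when dropout is equal, and then this analysis is not triggered. Once triggered, the runs separate and one may match or exceed the main estimate.

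A reader might also infer that the range will usually exclude the main estimate. At 24% / 36% and δ = 0.35 this happens in 55% to 58% of triggered trials on the coefficient scale. On the SAP's own d-from-t scale it happens in 0% to about 18%, depending on how the main d is formed. With wider gaps or a smaller effect it is about 20% to 32% on the coefficient scale. This is not a dependable consequence.

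Other points on the SAP's side:
- The example can be read as more leavers of the same kind in the control arm. If leavers in both arms truly sit at the pooled 75th percentile, the 75th run is the correct one: at 20% / 40% and a completer effect of 0.30, run and truth are both -0.341 while the main analysis gives -0.30. This stands. Whether a run is closer to the truth depends on the scenario, so the property cannot be claimed in general.
- The SAP does not say that condition is left out. Within-arm percentiles, or residuals and predictions from the analysis model, would remove the shrinkage. This also stands, but speaking of one lower and one higher value for all dropouts points to a common fill, and the two readings give differently centred ranges.
- It is a conditional, secondary analysis and the main results are reported regardless. A reader should not infer that the runs replace the main estimate or its test.
- Carrying the full treatment effect into dropouts is itself untestable. That is why the repair must be worded as an assumption.

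**Conclusion.** The point holds in limited form. On the natural reading, both runs assume no treatment effect among dropouts, and their midpoint is pulled toward zero by about the mean missing fraction: about 30% at an assumed 24% / 36% on the coefficient scale, less on the d scale. The individual runs lie either side of that midpoint by the dropout gap times the percentile.

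They are therefore not lower- and upper-end effect sizes, and the claim of less bias is unsupported. If data are missing at random, the imputed main analysis is unbiased and the centre of the runs is not. If control leavers worsened more than BRAVE leavers, no run can show it.

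The sizes rest on the assumed effect and dropout rates and on a residual model without condition. The result affects how a conditional sensitivity analysis is built and described, not the primary test.

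**What to change.** 1. In step (1), state that residuals come from each outcome's own analysis model, with condition and baseline.
2. In step (3), fill each missing parent with the prediction for their own arm plus the percentile residual.
3. Add two runs in which the arms receive opposite percentiles: 25th in BRAVE with 75th in control, and the reverse.
4. Replace "providing a more unbiased estimate of the overall treatment effect in the presence of unequal dropout" with wording such as: these runs show how the estimate moves under stated assumptions about parents who drop out. Keep the imputed analysis as the main estimate.

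The cost is one model term, a few sentences and two more runs per outcome, only when the dropout test is significant. No new data are needed. The downside is a wider reported range: in the worked case, about -0.75 to +0.05 instead of -0.32 to -0.16.

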To address *hypothesis 4*, a multiple linear regression with intervention condition (1=ORR+Project Brave; 0= ORR+waitlist control) and baseline parental distress in the context of child negative affect as predictor variables will indicate whether ORR+Project BRAVE versus ORR+delayed SSI led to greater reductions in parental distress from baseline to 2-week follow up. Parental distress will be indicated by the sum score of the distress tolerance scale. A p-value of $<.05$ will indicate a significant change in parental distress in the context of child negative affect from baseline to 2-week follow up.

Testing Assumptions

To justify the use of linear regression models for the purpose of prediction, we will check the following principle assumptions: 1) linearity and additivity of the relationship between dependent and independent variables, 2) statistical independence of the errors, 3) homoscedasticity of the errors, 4) normality of the error distribution. Nonlinearity will be tested by checking for a symmetric distribution of points on a plot of observed versus predictive values or residual versus predicted values. To check statistical independence of the errors, residual autocorrelations will be plotted to identify values that fall outside the 95% confidence band around zero. Homoscedasticity will be checked by plotting the residuals versus the predicted

values to examine the distribution of residual scores. Finally, normally distributed errors will be checked via normal probability plot to measure skewness and kurtosis.

Missing Data

We will impute any missing data using the expectation-maximization and bootstrapping algorithm implemented with Amelia II in R after running a sensitivity analysis to ensure that data is not missing at random. These imputed datasets allow for more conservative intent-to-treat analyses than listwise deletion or last-observation carried forward. We plan to impute as many datasets as there are percent of missing data for an outcome – rounding up to the next highest percentage (e.g., If 2.4% of data is missing on an outcome, we will create 3 imputed datasets). This process will allow us to retain high power even in the presence of missing data. Cohen's d effect sizes and 95% confidence intervals for analyses will be calculated using t -values for the treatment effects obtained from the analyses with the MOTE package in R.

False Discovery Rate

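### The exploratory moderation tests take over the Amelia II imputation without providing for the condition-by-moderator interaction; read literally, this shrinks any true interaction toward zero

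*SAP*

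**What the plan says.** - **SAP, Exploratory Moderation Tests:** "We will also conduct exploratory moderation tests examining various baseline variables as moderators of the SSI's impact on outcome". The tests are to be done "using the same approaches to missing data and corrections for multiple tests as described elsewhere in the pre-registration". No moderators are named.
- **SAP, Missing Data:** "We will impute any missing data using the expectation-maximization and bootstrapping algorithm implemented with Amelia II in R". The number of datasets follows the missing share: "We plan to impute as many datasets as there are percent of missing data for an outcome". The section prefers imputation to dropping incomplete cases and gives preservation of power as a reason. It does not list the variables in the imputation model.
- **SAP, Analytic Plan:** the hypothesis 1 model is "a multiple linear regression with intervention condition (1=ORR+Project Brave; 0=ORR+waitlist control) and baseline accommodation levels". The hypothesis 4 model has the same form. Neither contains an interaction.
- **SAP, Sample Size Justification:** "The target sample of 300 (150 per SSI condition accounting for attrition". Attrition is expected, but no rate is given. The 2.4% in the Missing Data section is only an example of the rounding rule.

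**The concern.** An imputation model should contain every relationship that the analysis will test. Amelia II draws missing values from a joint multivariate-normal model. Unless a product term is supplied as an extra variable, or the arms are imputed separately, the imputed outcome depends on condition and moderator additively. The imputed part of the sample then carries an interaction of zero, and the moderation regression averages it with the observed part.

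This would undo the SAP's own reason for imputing. For these tests the procedure would have less power than the listwise deletion it is meant to improve on. The false-discovery-rate correction, which also carries over, would then act on p-values that are already too large. The SAP's sensitivity analysis for unequal dropout would not reveal the problem. It runs only when dropout differs by condition, and it gives all dropouts one fixed residual-change value per run, so it carries no interaction either.

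**Working it through.** **The plan's own figures.** The SAP gives no figure for moderation or for the missing share. Its only related calculation is the sample size, "power = 0.80 were 395, 55, and 25, respectively for the primary outcome (hypothesis 1". A noncentral-F calculation for one tested predictor returns 395, 55 and 25 at f² = 0.02, 0.15 and 0.35. That does not bear on this point.

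**Inputs from the SAP.** N = 300, 150 per arm; number of imputations equal to the percent missing; Amelia II.

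**Assumed inputs.** Missing share p of 10 to 40%; standardised, fully observed moderator; true interaction β = 0.30 per SD; residual SD 0.8; only the outcome missing; two-sided 5% tests before any false-discovery-rate correction.

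**Expected size.** With even dropout, a share 1 − p of the data carries interaction β and a share p carries 0:

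estimate ≈ (1 − p) × β + p × 0, so estimate / β ≈ 1 − p.

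**Simulation.** 500 trials per setting, bootstrap plus normal-regression imputation, Rubin's rules, dropout completely at random. The imputation model without the product includes the moderator as a main effect.

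| Missing | 1 − p | Ratio to true value, no product | Power, no product | Power, complete cases (same runs) | Ratio, product included | Power, product included |
|---|---|---|---|---|---|---|
| 10% | 0.90 | 0.88 | .78 | .84 | 1.02 | .86 |
| 20% | 0.80 | 0.77 | .62 | .80 | 1.00 | .82 |
| 30% | 0.70 | 0.68 | .46 | .73 | 1.00 | .75 |
| 40% | 0.60 | 0.60 | .29 | .70 | 1.00 | .69 |

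Leaving the moderator out of the imputation model altogether gives 0.90, 0.78, 0.70 and 0.59. A separate simulation with a true interaction of −0.30 gave −0.269, −0.235, −0.213 and −0.182. Divided by −0.30, these are 0.90, 0.78, 0.71 and 0.61. Its power at 30% missing was .51, against .77 for complete cases.

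**Low missing shares** (residual SD 0.85). At 2.4% missing the ratio is 1.00 (power .84 against .87 for complete cases). At 5% it is 0.95 (.82 against .86).

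**Uneven dropout, 30% missing overall.**
- *45% in one arm and 15% in the other.* The imputed slope is common to both arms and sits .55 / (.55 + .85) = .393 of the way from one arm's slope to the other's. The ratio is (.55 + .45 × .393) − (.15 × .393) = .727 − .059 = .67. Simulated: 0.65.
- *Dropout rising with the moderator.* Simulated: 0.66.
- *Dropout of 60% beyond 1 SD of the moderator and 16% within it.* What counts is the share of the moderator's variance that remains observed. For a normal moderator, .801 of the variance lies beyond 1 SD and .199 within. The ratio is .801 × .40 + .199 × .84 = .320 + .167 = .49. Simulated: 0.47.

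**No true interaction, 30% missing** (800 trials). The mean estimate is about 0, so there is no bias. The type I error is 0.9% without the product and 4.9% with it. The test is too conservative because the pooled standard error is too large: with a true interaction at 30% missing, it averages .108 against an actual SD of .080.

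**Imputing by arm.** With a true value of −0.30, this gave −0.304, −0.300, −0.303 and −0.292 at 10, 20, 30 and 40% missing. Power at 30% was .745, against .742 for complete cases.

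**The case against.** The strongest objection is that the SAP never says the product is left out. It names a method and a rule for the number of datasets. Taking over the same approach fixes the method, not the same datasets or variable list, and a product can be supplied to Amelia II as a further variable. An analyst who did that would comply with the SAP. This stands: the missing term is inferred from silence. But the SAP gives that analyst no prompt, and the only regressions the imputation is described for contain no interaction, so the literal route leads to the biased version.

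The objection also rules out some stronger readings that a reader might infer:
- *Every interaction is shrunk.* A null interaction is not biased; it is only tested too conservatively.
- *The shrinkage always equals the missing share.* That holds for even dropout. It was 53% at 30% missing when dropout concentrated at extreme moderator values.
- *The moderation results will be wrong and real moderators reported as absent.* This depends on an assumed imputation model and an unknown missing share. At 5% missing or less the effect is minor.
- *The trial's main results are in doubt.* Hypotheses 1 to 4 test no interaction, and the moderation tests are labelled exploratory.

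The error is also conservative, so it would not produce false claims of moderation. That lowers the stakes but does not justify a test with less power than complete-case analysis.

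**Conclusion.** The point holds as a conditional one. The SAP applies its Amelia II approach to the moderation tests without providing for the interaction. Read literally, any true interaction shrinks toward zero, by about the missing share under even dropout and possibly by more otherwise. The test becomes too conservative and loses power relative to complete cases: about .46 to .51 against .73 to .77 at 30% missing. The size rests on the assumed missing share, the assumed interaction of 0.30 per SD, N = 300 and fully observed moderators. The documents do not support saying that the SAP prescribes a wrong imputation model. This is a cheap improvement to exploratory analyses, with no consequence for hypotheses 1 to 4.

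**What to change.** Add one sentence to Exploratory Moderation Tests, choosing either option:

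1. For the moderation tests, Amelia II is run separately in each arm, with the same number of imputations in both, and the completed data are stacked. This preserves condition-by-baseline interactions without naming moderators in advance.
2. For each moderation test, the imputation model includes the moderator and its product with condition.

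Both removed the bias in simulation. The change can be confined to the moderation tests; the imputation for hypotheses 1 to 4 need not be altered.

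The cost is slightly more analysis work. Under option 1, each imputation model is fitted on about 150 parents instead of 300. The simulations showed no material loss from this, but they used few variables, and the SAP does not list those it will impute with. Option 2 needs a separate imputation run for each moderator, or one run that carries all the products.
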